expression data is already well identified so we will not repeat this analysis on the esophageal samples, at least initially. Our first objective will be to identify disease specific transcript profiles that distinguish EG from controls and EC from controls. We will then correlate the pattern of gene expression in each disease with tissue eosinophil level for each disease. Furthermore, we will use the histology scoring tools described in Aim 1 to assess the correlation of dysregulated genes and other EoE-, EG-, and EC-related tissue features. During this process, the stringency levels (such as FDR, fold change, P value, etc.) will be interactively adjusted to yield a balance between gene of interest (GOI) pool size and positive prediction. The final leads selection should also be performed in the light of a comprehensive pathway analysis and principle component analysis to guarantee multiple biological processes coverage and minimal redundancy. The resulting GOI pool will be subsequently validated by qPCR and/or protein detection, at least for some of the major GOIs. Based on the identified disease specific genes, and those that track with specific disease characteristics such as tissue levels of eosinophils, mast cells, remodeling, mucus, and cellular hyperplasia, we will embed a set of diagnostic genes into a PCR-based high throughput fluid card, as we recently reported for the development of the EoE Diagnostic Panel (EDP)⁷. An EG diagnostic panel (EG-DP) and EC diagnostic panel (EC-DP) has potential to transform the field as it has potential for rapid, sensitive, specific diagnosis, and can provide information not readily apparent on initial microscopic analysis, as reported for the EoE-DP. It is noteworthy to point out that this potentially transformative undertaking could be scaled for general usage in the field.

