4.2.3 Exploratory Endpoints

The study subjects utilized for the exploratory analyses will be the same as those recruited in Aim 1, but the exploratory study will be limited to analysis of 20 samples from each subject group with active diseases and no therapy, as well as respective control samples (tissue from subjects that have normal histology and no history of any GI disorder).

Additionally, financial resources limit performance of gene expression profiles on all patients enrolled in this study. It is important to point out that all patients will have biopsy samples collected as part of SOC and will have archived FFPE specimens available. All subjects will be given the option to donate additional biopsies for RNA analysis. So, we will be in a position to subsequently analyze specific genes in follow up validation studies and/or to test specific hypotheses that may later develop such as those about particular patient phenotypes. If the subject subsequently undergoes successful therapy, we will also assess his/her second biopsy for changes in the mRNA

transcript profile following SOC treatment. EoE, EG, and EC as well as resolution of EoE, EG, and EC will be defined as in Aim 1. Patients who consent to the procurement of an extra biopsy sample, will have two research biopsies collected in RNALater and shipped to the [name] lab. Since EG and EC are not yet well characterized, and based on our preliminary analysis that gastric tissue has minimal overlap with the EoE transcriptome, we will initially focus on taking a genome wide approach using commercial high density expression chips. As a control, we will analyze the tissue specific transcriptome for gastric and colonic biopsy tissue from subjects who underwent endoscopy for workup of EGID (EG and EC) who subsequently were found to not have EGID or other pathology and no history of prior gastrointestinal disease. The analyses will be controlled for age, gender, and other parameters. Samples will be analyzed from FFPE tissue and fresh RNA, similar to the samples from diseased tissue.

5 Study Population

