AIM 2: Data analysis and statistical methods for EG and EC will be accomplished as previously reported for EoE^{26, 36}. In brief, individual array quality analyses, normalization, referencing, detection of differences at the exon level, and hierarchical and other clustering approaches are carried out using BioConductor, R, and GeneSpring version v7.3.1 (Agilent, Santa Clara, CA) software as detailed previously²⁶. To determine whether GOIs are also associated with tissue eosinophilia and COMs, we will use either Pearson or Spearman correlations for quantitative variables depending on the variable's distributional properties. Dichotomous outcomes t-tests or Mann-Whitney U will be used for comparisons. To determine the appropriate number of individuals (power), we used MD Anderson's Sample Size for Microarray Experiments. Assuming 30,000 genes and that some genes analyzed will not reach minimal expression levels, a sample size of 20 per group will yield 80% power to detect at least 2-fold differences with no more than 10 false positives. Given the exploratory nature of this Aim, we feel that this sample size appropriately balances statistical power with the currently available resources. Of note, depending upon the findings, results will be validated with qPCR and replication could be performed using additional resources available to CEGIR.

13 Quality Control and Quality Assurance

Training of observational study staff will be conducted by representatives of the DMCC and NIAID prior to beginning recruitment. All staff members will be required to complete certification and quality control in all applicable procedures as outlined in the MOO. The site principal investigators and coordinator(s) will be responsible for ensuring that all procedures are performed according to the protocol. Periodic reviews of procedures will be conducted by the coordinator or other trained personnel according to an individual schedule for each staff member, which is based on the activities he/she is responsible for conducting. Details of the quality control plan, including certifications and quality control of study procedures, are provided in the MOO.

14 Ethics/Protection of Human Subjects

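### Section 4.2.3 promises that the gene-expression analyses are controlled for age and gender, but the tests section 12.5 names for gene-of-interest associations take no covariates

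*Protocol*

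**What the plan says.** Protocol section 4.2.3 limits the transcriptome work to 20 samples per subject group plus control samples, then commits: "The analyses will be controlled for age, gender, and other parameters". It does not say how. It also says that both FFPE tissue and fresh RNA will be analysed.

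Protocol section 12.5, Aim 2, names these methods:

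- Array analysis by reference to earlier work: "Data analysis and statistical methods for EG and EC will be accomplished as previously reported for EoE". The steps listed include "detection of differences at the exon level, and hierarchical and other clustering approaches are carried out using BioConductor, R, and GeneSpring". No model is given.
- For genes of interest against eosinophilia and COMs: "we will use either Pearson or Spearman correlations for quantitative variables".
- For two-category variables: "Dichotomous outcomes t-tests or Mann-Whitney U will be used for comparisons".
- Sample size: "a sample size of 20 per group will yield 80% power to detect at least 2-fold differences with no more than 10 false positives", assuming 30,000 genes. No covariate enters this calculation.

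Section 4.1 describes how the gene list is chosen: "the stringency levels (such as FDR, fold change, P value, etc.) will be interactively adjusted". It does not state the model either.

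Two other places give the contrast. For Aim 1, section 12.5 names a regression with sex, age group and further covariates. Section 5.10 states matching on gender, race/ethnicity and age, but only for the microbiome sub-study.

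**The concern.** Pearson, Spearman, t-test and Mann-Whitney U all compare raw values. If they are run as written, nothing in the gene-of-interest associations controls for age or gender, and the commitment in section 4.2.3 is not met at that step.

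Age is the obvious threat. Eligibility starts at 3 years and has no upper limit, and children and adults enter the same disease groups. If a gene's expression and the eosinophil count both differ between children and adults, the two will correlate across the mixed sample even when they are unrelated within each age group. No case-control imbalance is needed for this.

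At stake is which genes are reported as tracking eosinophilia or disease activity. Section 4.1 says that genes tracking disease characteristics will feed the EG and EC diagnostic panels.

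**Working it through.** **1. The plan's own figure.** The inputs in section 12.5 are 20 per group, 80% power, a 2-fold difference (1.0 on the log2 scale), 30,000 genes and at most 10 false positives. The per-gene two-sided alpha is 10/30,000 = 0.000333. No SD is given, so 20 per group cannot be reproduced outright. Solving n = 2(z₁₋α/₂ + z₀.₈)²·SD²/1² for n = 20 gives SD = 1/[(3.588 + 0.842)·√(2/20)] = 0.714 (normal approximation). With the noncentral t, power at n = 20 is 0.806 for SD 0.65 and 0.708 for SD 0.7. The stated figure is therefore plausible, and nothing here shows it to be wrong.

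**2. Confounding of a simple correlation.** Assume half adults and half children, and that both variables differ by δ within-group SDs between them, with no association within age group. The between-group variance is δ²/4, so the induced correlation is ρ = (δ²/4)/(1 + δ²/4). The Fisher approximation to the rejection rate at nominal 5% is P(|Z + atanh(ρ)·√(n−3)| > 1.96).

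| δ | ρ | n = 20, Fisher | n = 40, Fisher |
|---|---|---|---|
| 0.5 SD | 0.0625/1.0625 = 0.059 | 6% | 6% |
| 1.0 SD | 0.25/1.25 = 0.20 | 13% | 23% |
| 1.5 SD | 0.5625/1.5625 = 0.36 | 34% | 63% |

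For δ = 1, atanh(0.20) = 0.203. Multiplied by √17 this is 0.84 and by √37 it is 1.23, which gives the 13% and 23% shown. Direct simulation of the Pearson test gives 14% and 24% at δ = 1, and about 38% and 67% at δ = 1.5. With adjustment for age group the simulated rate returns to about 5% throughout. Here n = 20 is one subject group and n = 40 is two groups' worth of samples.

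**3. Two-group tests, if the array step is also unadjusted.** Take a gene with no disease effect, an adult/child difference of 1 log2 unit, an assumed SD of 0.7, 20 per group and alpha 0.000333. The last column assumes independent groups drawn from a population with half adults.

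| Adults, group 1 v group 2 | Unadjusted false-positive rate | Chance of a gap this large or larger |
|---|---|---|
| 60% v 40% | 0.0002 (no inflation) | 27% |
| 70% v 30% | 0.0044 (13 times nominal) | 1.7% |
| 80% v 20% | 0.050 (150 times nominal) | 0.02% |

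Material inflation thus needs an imbalance that chance rarely produces. Unmatched recruitment of controls could produce one, but the protocol gives no age mix. With equal mixes there is no inflation, but leaving this age effect out of the model lowers power for a true 2-fold gene from 0.71 to 0.38.

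**4. Cost of adjusting.** With balanced groups and two covariates (residual df 36 instead of 38), power goes from 0.806 to 0.800 at SD 0.65 and from 0.708 to 0.701 at SD 0.7. If the adult share differs by g around 50%, the standard error grows by 1/√(1−g²): 2% at 60 v 40, 9% at 70 v 30 and 25% at 80 v 20. At SD 0.65, with one age covariate, power is then about 0.69 at 70 v 30 and 0.49 at 80 v 20.

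**The case against.** The strongest reply is that section 12.5 does not confine Aim 2 to simple tests. It also names an array-level search for differences, by reference to earlier reports, and nothing in the protocol shows that this step leaves out age. This stands. The correlations apply to genes already chosen: "To determine whether GOIs are also associated with tissue eosinophilia and COMs, we will use either Pearson or Spearman correlations for quantitative variables". A reader might infer that age-related genes therefore enter or drop out of the gene list because of these tests. The text does not support that: the list is built earlier, by a step whose model is not stated. Reading the sentence on dichotomous outcomes as the case-control screen is one interpretation only.

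A second reply is that controlling for age could mean matching or restricting samples, so the two sections do not flatly contradict each other. That is possible, but the protocol states no matching for this analysis. Matching controls to cases would protect the two-group comparison; it would not remove age from a correlation computed across a mixed-age group.

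Third, Aim 2 is called exploratory, with qPCR validation and possible replication. This lowers the stakes. However, qPCR on the same samples would reproduce a confounded association, not expose it.

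Fourth, several symptom scores are specific to children or adults and so are partly stratified by age. This is true of SODA and PUCAI, for example. Eosinophil counts and the Lanza and UCCIS scores cover both age groups (Table 1 in section 4.2.1).

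Finally, methods detail often sits in a statistical analysis plan, which is not at hand. Here, though, the protocol does name the tests, and those tests cannot by themselves deliver what section 4.2.3 promises.

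**Conclusion.** The point holds for the gene-of-interest associations. Section 4.2.3 commits to control for age and gender, the tests in section 12.5 do not provide it, and no other means is stated for Aim 2. The two sections need reconciling.

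The size depends on assumptions, because the protocol gives no age mix, age effect or SD. With an equal adult/child mix and a 1 SD difference in both variables, the false-positive rate at nominal 5% is about 14% (n = 20) to 24% (n = 40). At 0.5 SD the excess is slight; at 1.5 SD it is large.

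Bias in the gene list follows only if the array step is also unadjusted and the groups differ in age. Counts of extra false-positive genes should not be quoted as expected consequences: they rest on assumed age effects and on imbalances that chance seldom produces. No figure stated in the protocol is shown to be wrong.

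**What to change.** In section 12.5, Aim 2:

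- Replace the simple correlations and two-sample tests for gene-of-interest associations with partial (or partial rank) correlations, or regression, including age and sex. Add specimen type where FFPE and fresh samples are pooled.
- State that the per-gene disease-versus-control model includes the same covariates.
- Keep the unadjusted results as a supplement.
- Name the other parameters that section 4.2.3 leaves open.

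Age and sex are already collected, so the change is one of wording. It uses two to three degrees of freedom. The power loss is small when groups are balanced but substantial if the age mix differs strongly between cases and controls, as the last working step shows. Similar age mixes when the 20 samples per group are chosen would limit that loss.

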14.1 The Belmont Report

In accordance with the National Institutes of Health's federal wide assurance ([FWA00005897](#)): "This institution assures that all of its activities related to human subject research, regardless of funding source, will be guided by the ethical principles of The Belmont Report." Additionally, the investigator assures that all activities of this protocol will be guided by the ethical principles of The Belmont Report, 45 CFR 46 and all of its subparts (A, B, C and D).

14.2 Institutional Review Board

A copy of the protocol, informed consent forms, assent form, any advertising/recruitment materials and other information to be completed by participants, such as survey instruments or questionnaires, will be submitted to the IRB for written approval.

The investigator must submit and obtain approval from the IRB for all subsequent amendments to the protocol, informed consent documents and other study documentation referenced above. The investigator will be responsible for obtaining IRB approval of the annual Continuing Review throughout the duration of the study.

The investigator will notify the IRB of serious adverse events and protocol violations.

14.3 Informed Consent Process

Written informed consent will be obtained from each participant before any study-specific procedures or assessments are done and after the aims, methods, anticipated benefits, and potential hazards are explained. The research study will be explained in lay terms to each potential research participant. The participant's willingness to participate in the study will be documented in writing in a consent form, which will be signed by the participant with the date of that signature indicated. The investigator will keep the original consent forms and signed copies will be given to the participants. It will also be explained to the participants that they are free to refuse entry into the study and free to withdraw from the study at any time without prejudice to future treatment. Written and/or oral information about the study in a language understandable by the participant will be given to all participants.

Once the informed consent has been signed, the participant is considered enrolled in the study.

14.3.1 Assent or Informed Consent Process (in Case of a Minor)

All participants will receive a full oral explanation of the study, and informed consent will be obtained prior to participation. The consent form that is used for this study will be approved by a central IRB. Informed consent will be obtained by one of the investigators or his/her authorized delegate. All study staff receive training in the informed consent process. Prospective subjects are given time to read over the entire consent form in order to make their decision and are also given

an opportunity to ask any questions concerning the study. They may request what they would like done with their material and clinical information when the study is completed, or if they should happen to withdraw from the study. They are then asked to check boxes indicating the components of the study to which they will consent; for example, some individuals can participate in database entry but not consent for tissue procurement. If the child is over the age of assent (varies by institution), they are also asked to sign an assent form. A copy of the consent/assent form is given to the family so that they have the information regarding the study. Another copy is placed in their medical chart, and the third copy is kept in the research office.

14.4 Participant Confidentiality

All of the practices will adhere to institutional and national policies regarding the Health Insurance Portability and Accountability Act of 1996 (HIPAA).

Following Health Insurance Portability and Accountability Act guidelines, a participant's privacy and confidentiality will be respected throughout the observational study. Each participant will be assigned a sequential identification number, and this number rather than a name will be used to collect, store, and report participant information. Data reported in medical journals or scientific meetings will be presented in aggregate for participants as a whole. No individual participant will be identified in any way.

Participant confidentiality will be strictly held in trust by the participating investigators, their staff, and the sponsor(s) and their agents. This confidentiality is extended to cover testing of biologic samples in addition to the clinical information relating to participating subjects.

Research samples will be labeled with code numbers so that direct identifiers will not be visible. All information concerning patient identification will be kept in protected storage areas, including password-protected computer files and locked files and/or offices. The Principal Investigator, primary researchers, and clinical research coordinator(s) will have access to the patient identifiers

Some samples that are collected during an endoscopy and/or colonoscopy for research purposes may be frozen and shipped to other hospitals, institutions, and testing companies for analysis. Data may also be shared. The data and/or samples will be coded with indirect identifiers per HIPAA and have no PHI associated with them. The data and/or samples will be used in a collaborative relationship between institutions, or testing company receiving the data and/or samples. All of these samples will be shared under an MTA, or other applicable agreement.

14.5 Transfer of Data to DMCC and Federal data repository

The clinical information collected for this study will be stored at the Data Management and Coordinating Center at the University of South Florida in Tampa, FL and also sent to a Federal data repository.

14.6 Registration on ClinicalTrials.gov

A description of this study will be available on <http://www.ClinicalTrials.gov>.

14.7 Study Discontinuation

This study will not have study discontinuation rules as it is an observational study. The NIH and local IRBs (at their local site) have the authority to stop or suspend this trial at any time.

15 Data Handling and Record Keeping

15.1 Data Management Responsibilities

All study data will be collected via systems created in collaboration with the RDCRN Data Management and Coordinating Center and will comply with all applicable guidelines regarding patient confidentiality and data integrity. Data retained by DMCC will be returned at study completion to the CEGIR.

15.2 Data Capture Methods

Clinical features of subjects will be determined during SOC evaluation as well as a REGID (Registry for Eosinophilic GI Diseases) Intake Form. The REGID Intake Form includes self-reported demographic, race/ethnicity, exposure and clinical. In order to effectively store and integrate all of the collected data, we will utilize the REGID infrastructure located at the Biomedical Informatics Division at CCHMC. The division has locally implemented the i2b2 (Informatics for Integrating Biology and the Bedside; Research Data Warehouse) for use by the research community. i2b2 is an NIH-supported National Center for Biomedical Computing which represents a scalable informatics framework designed for translational research that is based upon Research Patient Data Registry developed at Massachusetts General Hospital (1). It is designed primarily for cohort identification from a deep data repository derived from all of clinical data in a hospital electronic medical record, and provides researchers with summaries of de-identified data, as based upon *ad hoc* user queries. i2b2 provides the underlying data warehouse for REGID which currently provides for a web-based research registry. Standard templates within REGID have been developed so that valid and reliable clinical data are captured for each clinical encounter for deposit into the i2b2 data warehouse inclusive of the pediatric PROs (Pediatric Eosinophilic Esophagitis Symptom Score, PEES v2.0, PedsQL EoE Module). We can utilize REGID to incorporate new data sets (e.g. Eosinophilic Esophagitis Activity Index, EEsAI, Clinical Trial Identifier: NCT00939263).

15.2.1 Registration

Registration of participants in this protocol will employ an interactive data system in which the clinical site will attest to the participant's eligibility as per protocol criteria and obtain appropriate informed consent. IRB approval for the protocol must be on file at the DMCC before accrual can occur from the clinical site.

The DMCC will use a system of coded identifiers to protect participant confidentiality and safety. Each participant enrolled will be assigned a local identifier by the enrollment site. This number can be a combination of the site identifier (location code) and a serial accession number. Only the registering site will have access to the linkage between this number and the personal identifier of the subject. When the participant is registered to participate in the study, using the DMCC provided web-based registration system, the system will assign a participant ID number. Thus each participant will have two codes: the local one that can be used by the registering site to obtain personal identifiers and a second code assigned by the DMCC. For all data transfers to the DMCC both numbers will be required to uniquely identify the subject. In this fashion, it is possible to protect against data keying errors, digit transposition or other mistakes when identifying a participant for data entry since the numbers should match to properly identify the participant.

